7.1 Primary Analysis Set

The Primary Analysis Set (PAS) will include all randomized subjects. The analysis will be conducted according to the original randomization assignment regardless of the actual treatment received during the study (as per intent-to-treat principle). All the primary, secondary, and exploratory efficacy endpoints will be evaluated on the Primary Analysis Set, unless otherwise specified.

7.2 Full Analysis Set

The Full Analysis Set (FAS) includes all the subjects who have enrolled in the run-in period.

7.3 Disease-Worsening Analysis Set

The Disease-Worsening Analysis Set includes randomized subjects who meet the definition of Disease-Worsening at any point after randomization.

7.4 Rescue Analysis Set

This includes randomized subjects who meet the definition of Disease-Worsening and have received both at least one dose of active rescue therapy etanercept and at least one dose active rescue therapy methoxrexate as recorded in the eCRF.

7.5 Run-In Failure Analysis Set

The Run-In Failure Analysis Set includes all enrolled subjects who do not complete run-in due to failing to meet Part 2 Inclusion Criteria or due to fulfilling Part 2 Exclusion Criteria per Sections 4.2.1 and 4.2.2, respectively, in the protocol.

7.6 Run-In Safety Analysis Set

The Run-In Safety Analysis Set includes all enrolled subjects who received at least one dose of open label run-in etanercept and/or at least one dose of open label run-in methotrexate (as specified in the eCRF).

7.7 Post-Run-In Safety Analysis Set

The Post-Run-In Safety Analysis Set includes all subjects who received at least one dose of any investigational product after randomization.

8. Subgroup Analyses

Subgroup analyses, which would be considered exploratory, may be performed if an examination of the covariates in [Section 4.2](#) suggests that any treatment difference for the primary and secondary endpoints depends on any baseline covariates.

9. Interim Analysis and Early Stopping Guidelines

No interim analysis is planned for this study.

10. Data Screening and Acceptance

10.1 General Principles

The objective of the data screening is to assess the quantity, quality and statistical characteristics of the data relative to the requirements of the planned analyses.

10.2 Data Handling and Electronic Transfer of Data

The Amgen Global Study Operations-Data Management (GSO-DM) department will provide all data to be used in the planned analyses.

10.3 Handling of Missing and Incomplete Data

Subjects may be missing specific data points for a variety of reasons. In general, data may be missing due to a subject's early withdrawal from study, a missed visit, or inability to evaluate an endpoint at a particular point in time. The general procedures outlined below describe what will be done when a data point is missing.

10.3.1 Missing Baseline Evaluation

Missing baseline evaluations will not be imputed.

10.3.2 Missing Post-Baseline Evaluation

See [Section 11.5](#).

10.3.3 Missing Components of Composite Endpoints

Missing components of composite endpoints will not be imputed.

10.3.4 Missing and Incomplete Dates

For any listings, missing or incomplete dates will be listed as is. No imputation will be done on incomplete stop date of an adverse event unless specified otherwise.

In the case where the start or stop date of an event or medication is missing or incomplete, the following rule will be applied:

	Missing	Imputation	Exception
Start date (AE, concomitant medication)	Day	01	Default to Study Day 1 if an event starts the same year and month as Study Day 1 and Stop date is after Study Day 1
	Day/Month	01JAN	Default to Study Day 1 if an event started the same year as Day1 and Stop date is after Study Day 1
	Day/Month/Year	No imputation	
Stop date (concomitant medication)	Day	Last day of the month	Default to the End of Study Date or the primary analysis cut-off date for ongoing subjects if the concomitant medication stopped the same year and month as the End of Study Date or primary analysis cut-off date
	Day/Month	31DEC	Default to the End of Study Date or the primary analysis cut-off date for ongoing subjects if the concomitant medication stopped the same year as the End of Study Date or primary analysis cut-off date
	Day/Month/Year	No imputation	

In case a subject dies during the study, impute the missing AE and CM end dates using the subject's date of death.

10.4 Detection of Bias

Subject selection and treatment group allocation were performed in a manner minimizing potential bias. Assessing endpoints and handling withdrawals were done without knowledge of treatment group. Other factors that may introduce bias include:

- Important protocol deviations likely to impact the analysis or interpretation of results;
- Breaking blind before database lock and formal unblinding;
- IP dosing non-compliance;
- Reasons for early withdrawal from treatment or from study.

The incidence of these factors will be assessed. Important protocol deviations likely to impact the analysis and interpretation of results will be listed and/or tabulated in the

Clinical Study Report (CSR). If a significant number of major protocol deviations are observed, an additional sensitivity analysis may be performed on the efficacy data excluding subjects with major protocol deviations.

Any breaking of the blind for individual subjects prior to formal unblinding of the study will be documented in the CSR, including the timing and reason for unblinding. The impact of such unblinding on the results will be assessed.

Tabulations of important protocol deviations (IPDs) related to IP dosing non-compliance by treatment group will be provided.

Reasons for early withdrawals from treatment and from study will be summarized. If a significant pattern is observed, additional sensitivity analyses may be performed on efficacy data adjusting for reasons for early withdrawal.

10.5 Outliers

Descriptive summaries will be examined to identify unexpected values. Outliers due to data entry errors will be corrected by the study team before data lock. Outliers that are not due to data entry will be included in the analysis. If it is deemed necessary after the team reviews the output from the planned analyses after data lock, a post-hoc sensitivity analysis excluding subjects with outliers may be performed.

10.6 Distributional Characteristics

The Chi-squared test with continuity correction allows for analysis of categorical endpoints even when some or all contingency cells have less than 5 subjects. The t-test used for continuous endpoints assumes that the means of two independent populations follow normal distributions. With all three treatment arms having more than 30 subjects, this assumption is fair per the central limit theorem. When standard deviations are statistically significantly different as identified by an F-test with p-value less than or equal to 0.05, the Satterthwaite approximation is used.

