Using an assumed attrition rate of 30% in the open-label run-in period, due to exclusion of subjects with Disease-Worsening during the run-in period, or other reasons, approximately 358 subjects will be enrolled in order to have approximately 250 subjects randomized in a 2:2:1 ratio to one of three treatment groups: etanercept monotherapy (n = 100), methotrexate monotherapy (n = 100) and etanercept plus methotrexate combination therapy (n = 50). Amgen may choose to alter the sample size of subjects enrolled in order to ensure that approximately 250 subjects are randomized to treatment.

4. Study Endpoints and Covariates

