11.1 General Considerations

The primary analysis will be performed after all subjects have completed the Week 48/ET assessment and the 30-day safety follow-up period and all data have been finalized.

Subject disposition, demographics, and baseline disease characteristics will be summarized descriptively by randomized treatment group.

For categorical endpoints, descriptive statistics will report frequency and percentage. For continuous endpoints, descriptive statistics will include the number of observations, mean, standard error or standard deviation, median, minimum, and maximum.

The statistical test for the primary efficacy endpoint will have a significance level of 0.05. Non-responder imputation will be employed for the missing values of the primary endpoint.

For continuous secondary endpoints, t-tests will compare 1) etanercept monotherapy vs methotrexate monotherapy, and 2) etanercept and methotrexate combination therapy vs methotrexate monotherapy. No multiplicity adjustments will be made.

For binary secondary endpoints, Chi-squared tests with continuity correction will compare 1) etanercept monotherapy vs methotrexate monotherapy, and 2) etanercept and methotrexate combination therapy vs methotrexate monotherapy. No multiplicity adjustments will be made.

For time-to-event secondary endpoints, the number of subjects achieving the event and the number of subjects censored as defined in [Section 6.4](#) will be provided.

Kaplan-Meier (KM) curves, estimates, and 95% CIs will be provided by treatment group. A two-sided log-rank test incorporating treatment group will evaluate 1) etanercept monotherapy vs methotrexate monotherapy, and 2) etanercept and methotrexate combination therapy vs methotrexate monotherapy. Median time-to-event will be provided for each of the treatment arms.

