11.5.2 Secondary Efficacy Endpoint(s)

For secondary endpoints, unless otherwise noted, the Chi-squared test will be used for categorical endpoints, the t-test for continuous endpoints, and Log-rank test for time-to-event endpoints. In comparison of means, the Satterthwaite t-test may be used when variances between the two groups are different. These tests will evaluate etanercept monotherapy vs methotrexate monotherapy and etanercept and methotrexate combination therapy vs methotrexate monotherapy.

Proportion of subjects achieving SDAI remission at week 48 for the etanercept plus methotrexate treatment arm will be compared to that of the methotrexate monotherapy arm using the chi-squared test and will be presented with nominal p-values only (eg, no adjustment for multiplicity will be done). To parallel the the primary analysis of the primary estimand, the proportion of subjects in the etanercept plus methotrexate treatment arm and the methotrexate monotherapy arm achieving SDAI remission at week 48 will be evaluated using non-responder imputation, as observed data, and multiple imputation.

The proportion of subjects achieving SDAI remission (≤ 3.3), SDAI continuous score, and SDAI change from baseline at all visits will be summarized by treatment group using the PAS. Subjects with missing SDAI value at week 48 and subjects who disease-worsened are considered non-responders.

DAS28-ESR, DAS28-CRP, and CDAI, and their changes from baseline will also be summarized by visit for each treatment group using the PAS. Missing data will not be imputed for these continuous endpoints. T-tests will compare means between etanercept vs methotrexate and etanercept + methotrexate vs methotrexate.

Proportion of subjects achieving Boolean remission will be tabulated by visit for each treatment group using the PAS. Boolean remission using 28-joint-count, 28-joint-count + feet and ankles, and 66/68 joint count will be assessed.

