Patient Global Assessment of Joint Pain at all timepoints	Summary statistics for PtGAJP at each Analysis Visit for the PAS. T-test comparing etanercept monotherapy vs methotrexate monotherapy T-test comparing etanercept and methotrexate combination therapy vs methotrexate monotherapy	
SDAI LDA at all timepoints	Similar analysis as SDAI remission at all measured timepoints for the PAS.	
DAS28-ESR remission at all timepoints	Similar analysis as SDAI remission at all measured timepoints for the PAS.	
DAS28-ESR LDA at all timepoints	Similar analysis as SDAI remission at all measured timepoints for the PAS.	
DAS28-CRP remission at all timepoints	Similar analysis as SDAI remission at all measured timepoints for the PAS.	
Reason for Disease-Worsening	Observed count (percentage) of reason for disease-worsening at each Analysis Visit for the Disease-Worsening Analysis Set.	

Table 2. Exploratory Endpoints Summary Table

Endpoint	Primary Summary and Analysis Method	Exploratory Analysis
Exploratory Endpoints(Continued)		
SDAI score at Disease-Worsening	Summary statistics for the SDAI score at DW Date for the Disease-Worsening Analysis Set. T-test comparing etanercept monotherapy vs methotrexate monotherapy T-test comparing etanercept and methotrexate combination therapy vs methotrexate monotherapy	
Disease Activity at Disease-Worsening	Observed count (percentage) of subjects in each Disease Activity category (Low, Moderate, High) at DW Date for the Disease-Worsening Analysis Set. Chi-squared test comparing etanercept monotherapy vs methotrexate monotherapy Chi-squared test comparing etanercept and methotrexate combination therapy vs methotrexate monotherapy	
Observed SDAI remission at visits following rescue	Observed count (percentage) of subjects achieving observed SDAI remission by Rescue_Visit for the Rescue Analysis Set. Chi-squared test comparing etanercept monotherapy vs methotrexate monotherapy Chi-squared test comparing etanercept and methotrexate combination therapy vs methotrexate monotherapy	Similar to the Primary Analysis Method but using the Disease-Worsening Analysis Set and DW_Visit.
SDAI LDA at visits following rescue	Similar analysis as for SDAI remission at visits following rescue	Similar to the Primary Analysis Method but using the Disease-Worsening Analysis Set.

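### The SAP states two rules for choosing the t-test, and its over-30 argument for normal means does not reach the Disease-Worsening and Rescue Analysis Sets

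*SAP*

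**What the plan says.** SAP 10.6 (Distributional Characteristics) makes two separate statements about the t-test.

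- On normality of means: "With all three treatment arms having more than 30 subjects, this assumption is fair per the central limit theorem".
- On unequal variances: "When standard deviations are statistically significantly different as identified by an F-test" at p ≤ 0.05, the Satterthwaite version applies. The test used otherwise is not named; the ordinary pooled t-test is implied.

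SAP 11.5.2 then says that "the Satterthwaite t-test may be used when variances between the two groups are different", and 11.5.3 repeats this for the exploratory endpoints. Neither section mentions an F-test or a threshold.

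The t-test is used widely. SAP 11.1 states: "For continuous secondary endpoints, t-tests will compare 1) etanercept monotherapy vs methotrexate monotherapy", and adds combination v methotrexate, with no multiplicity adjustment. Table 1 applies this to SDAI, DAS28-ESR, DAS28-CRP and CDAI, as scores and changes, by visit. Table 2 also plans t-tests outside the full set: "Summary statistics for the SDAI score at DW Date for the Disease-Worsening Analysis Set" is followed by both pairwise t-tests, and SDAI by visit after rescue is treated the same way in the Rescue Analysis Set. Tables 1 and 2 do not say which t-test is meant.

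**The concern.** There are two weaknesses, and they are independent.

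First, the choice between pooled and Satterthwaite tests is mechanical in 10.6 and permissive in 11.5.2 and 11.5.3. Two programmers could report different p-values for the same endpoint and each be following the SAP. The gate itself can also distort the error rate when group sizes differ: if the F-test misses a real difference in SDs, the pooled test is used where it does not hold its level.

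Second, the central-limit argument concerns the randomized arms. Nothing comparable is offered for the subsets defined by worsening or rescue, where the combination arm should be small.

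At stake are the nominal p-values for continuous secondary endpoints (slightly) and those for the post-worsening exploratory comparisons (more).

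**Working it through.** **Arm sizes.** Allocation 2:2:1 of 250 gives 100/100/50. The 100 is reproducible from 72% v 50%, two-sided 0.05, 90% power:

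n = [1.960√(2 × 0.61 × 0.39) + 1.282√(0.72 × 0.28 + 0.50 × 0.50)]² / 0.22² = 101.2, so 102. The unpooled-variance version gives 99. All three randomized arms therefore exceed 30, as 10.6 says.

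**Subset sizes.** Under SAP 6.2 a subject who worsens cannot be a responder, so non-responders cap the Disease-Worsening Analysis Set. The Rescue Analysis Set (7.4) is contained in it. With the rates in SAP 3.2:

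- methotrexate: 100 × (1 − 0.50) = 50
- etanercept: 100 × (1 − 0.72) = 28 (95% binomial range 19–37; probability of 30 or fewer, 71%)
- combination: 50 × (1 − 0.861) = 7 to 50 × (1 − 0.783) = 11 (ranges 3–12 and 5–17)

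The combination arm would pass 30 only if more than 30/50 = 60% of it worsened.

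**Why the pooled test drifts.** Take 50 v 100 with the smaller arm's SD 1.25 times larger.

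- True variance of the difference: 1.5625/50 + 1/100 = 0.04125.
- Pooled estimate, on average: [(49 × 1.5625 + 99)/148] × (1/50 + 1/100) = 1.186 × 0.03 = 0.0356.
- The standard error is too small by a factor √(0.04125/0.0356) = 1.077, so the size is about 2[1 − Φ(1.96/1.077)] = 6.9%. Simulation gives 6.9%.
- The F-test detects this SD ratio 45% of the time, which pulls the gated rule back to 5.7%.

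**Type I error at nominal 5%, normal data.** Simulation under equal means, 100,000 replicates per setting. The SD ratio (other arm to methotrexate) runs from 0.5 to 2; this is an assumption, because the documents give no SDs.

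| Other arm v methotrexate | Gated rule | Always Welch |
|---|---|---|
| 100 v 100 | 5.0–5.2% | 5.0–5.2% |
| 50 v 100 | 4.5–5.7% | 4.8–5.1% |
| 28 v 50 | 4.4–5.9% | 5.0–5.1% |
| 11 v 50 | 3.4–8.4% | 5.0–5.2% |
| 7 v 50 | 3.1–10.6% | 5.2–5.5% |

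At 8 v 50 the gated rule gives 8.5% and 10.1% when the small arm's SD is 1.25 and 1.5 times larger. The upper ends arise because the F-test has little power here: it detects a 1.5-fold SD difference 43% of the time at 11 v 50 and 33% at 7 v 50.

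**Right-skewed data.** Lognormal, log-SD 0.8 (one assumed value), small arm's SD 1, 1.25 and 1.5 times that of methotrexate; 60,000 replicates per setting at 11 and 7 v 50, and 40,000 at 8 v 50.

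| Size | Gated rule | Always Welch |
|---|---|---|
| 11 v 50 | 7.9, 8.2, 8.9% | 7.9, 9.5, 10.3% |
| 8 v 50 (ratios 1.25–1.5 only) | 8.9–9.2% | 10.8–11.5% |
| 7 v 50 | 10.1, 9.0, 9.4% | 10.7, 11.7, 12.2% |

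In these sets Welch is no better than the gated rule. At 28 v 50 both stay near nominal over the same ratios (gated 4.9–6.4%, Welch 4.8–6.6%), so the problem lies mainly with the combination arm.

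**The case against.** The best defence is that 10.6 is a fully specified rule, that the later sections can be read as shorthand for it, and that little turns on the choice. Much of this stands. In the full set the distortion is under one percentage point, it affects only combination v methotrexate, and those tests are secondary with unadjusted p-values. The small-set tests are exploratory.

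Some stronger readings are tempting but unsupported:

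- *That arm size is the SAP's justification for the F-test.* It is not; 10.6 uses it only for normality of means.
- *That unequal allocation undermines every continuous comparison.* Etanercept v methotrexate is 1:1 in the full set, where pooled, gated and Welch tests agree.
- *That the analyst is free to choose after seeing results.* Section 10.6 is mechanical. The fault is that 11.5.2 and 11.5.3 do not match it.
- *That the F-test's sensitivity to skewness harms the full-set results.* A false rejection only sends the analysis to Satterthwaite. At 50 v 100 with equal SDs and lognormal data, the gated rule and Welch both run at 5.1%.
- *That Welch everywhere repairs the small sets.* Under skewness it does not.

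What the defence leaves unanswered is the mismatch between sections and the absence of any size argument for the two subsets.

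**Conclusion.** The point holds as a minor one. Two rules for the same choice need to be made one, and the over-30 argument should not be carried into the Disease-Worsening and Rescue Analysis Sets. The full-set cost is roughly half a point either way for combination v methotrexate (4.5–5.7%) and nil for etanercept v methotrexate. In sets with 8 to 11 combination subjects against 50, the gated rule runs at about 3–10% under normality with SD ratios 0.67 to 1.5. Under the assumed skewness, Welch runs at about 8–11% for ratios 1 to 1.5. The primary chi-squared test is not involved.

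These sizes rest on assumptions:

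- The SD ratios and the skewed distribution are assumed; the SAP gives neither.
- The combination rates come from two cited studies; the plan sets none for this arm.
- Those rates and the planned monotherapy rates are taken to apply to the SAP 6.2 endpoint, which requires no worsening. Non-response also includes missing data, so 7 to 11 and 28 are expected ceilings at those rates.

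**What to change.** 1. In SAP 10.6, delete the F-test sentence and specify the Satterthwaite (Welch) t-test, without a pre-test, for continuous comparisons in the Primary Analysis Set.
2. In 11.5.2 and 11.5.3, replace the permissive wording with the same statement.
3. Limit the over-30 statement in 10.6 to the Primary Analysis Set.
4. In Table 2 and the matching text of 11.5.3, replace the t-tests in the Disease-Worsening and Rescue Analysis Sets with descriptive statistics and confidence intervals, or with a rank or permutation test labelled exploratory.

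The cost is SAP wording; standard software prints both t-tests, and Welch loses essentially nothing at 100 v 100. The one real downside is that nominal exploratory p-values in the small sets are lost or replaced, and a rank test would not address the difference in means.

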10.7 Validation of Statistical Analyses

Programs will be developed and maintained, and output will be verified in accordance with current risk-based quality control procedures.

Tables, figures, and listings will be produced with validated standard macro programs to produce the specified outputs.

The production environment for statistical analyses consists of Amgen-supported versions of statistical analysis software, for example SAS System version 9.4 or later.

11. Statistical Methods of Analysis

11.1 General Considerations

The primary analysis will be performed after all subjects have completed the Week 48/ET assessment and the 30-day safety follow-up period and all data have been finalized.

Subject disposition, demographics, and baseline disease characteristics will be summarized descriptively by randomized treatment group.

For categorical endpoints, descriptive statistics will report frequency and percentage. For continuous endpoints, descriptive statistics will include the number of observations, mean, standard error or standard deviation, median, minimum, and maximum.

The statistical test for the primary efficacy endpoint will have a significance level of 0.05. Non-responder imputation will be employed for the missing values of the primary endpoint.

For continuous secondary endpoints, t-tests will compare 1) etanercept monotherapy vs methotrexate monotherapy, and 2) etanercept and methotrexate combination therapy vs methotrexate monotherapy. No multiplicity adjustments will be made.

For binary secondary endpoints, Chi-squared tests with continuity correction will compare 1) etanercept monotherapy vs methotrexate monotherapy, and 2) etanercept and methotrexate combination therapy vs methotrexate monotherapy. No multiplicity adjustments will be made.

For time-to-event secondary endpoints, the number of subjects achieving the event and the number of subjects censored as defined in [Section 6.4](#) will be provided.

Kaplan-Meier (KM) curves, estimates, and 95% CIs will be provided by treatment group. A two-sided log-rank test incorporating treatment group will evaluate 1) etanercept monotherapy vs methotrexate monotherapy, and 2) etanercept and methotrexate combination therapy vs methotrexate monotherapy. Median time-to-event will be provided for each of the treatment arms.

